Phototoxic potential of the infrared light source when cells are exposed to ABY-029 was evaluated, compared to a known FDA approved phototoxic agent benzoporphyrin derivative monoacid A (BPD-MA) and found to be negligible.

- **Imaging study for localization in U251 orthotopic xenograft glioma in mice and rats**

Rats or mice were inoculated with orthotopic implantations of a human glioma cell line (U251, F98 or F98-EGFR) or with PBS (control) in the brain. Tumors were allowed to grow for 2 – 3 weeks before carrying out fluorescent tracer experiments.

We demonstrated that ABY-029 penetrated further into the margin of a U251 orthotopic xenograft mouse model than did a fluorescently labelled antibody (IRDye 680RD-Erbilux) (Sexton et al, PLoS One 2013). Longitudinal imaging of mice bearing U251 xenografts grown orthotopically in the brain was performed by tracking the uptake and retention over 0-3 hours in order to mimic *in vivo* imaging in humans. A reference tracer composed of a non-specific Affibody molecule bound to IRDye 680RD (LI-COR Biosciences, Inc) was used to quantify blood vessel leakage versus ABY-029 binding to the tumor. We also quantified the

tumor to normal brain uptake as a function of time, and compared these results to direct fiber optic probe measurements *in situ* and *ex vivo*. We validated the concept that sufficiently high signal to noise is achievable for ABY-029 uptake in the xenograft tumor model for microdose injection levels. This study suggests that microdoses of the compound will be detectable via imaging in human studies.

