We used the U251 orthotopic xenograft rat model to demonstrate that distribution and uptake of microdose levels of ABY-029 is heterogeneous within a tumor, and that high fluorescing regions closely match with highly overexpressing regions of EGFR, as determined by immunohistochemistry (D'Souza et al, submitted 2016). We evaluated the uptake of the preGMP batch of ABY-029 in glioma after intravenous injection in normal rats. Fluorescent imaging of *ex vivo* brain slices from rats was conducted at different time points after ABY-029 administration (1 h – 48 h) to verify which time points provided maximal tumor to normal contrast. Although U251 tumor was most clearly visualized 1 hour after ABY-029 injection, tumors could be differentiated from the background after 48 hours. These results suggest that ABY-029 shows excellent potential to increase surgical visualization of confirmed EGFR positive tumors, with tumor to normal tissue contrast levels between 10 and 15.

We compared uptake of pre-GMP ABY-029 and in orthotopic rat model using both an EGFR negative tumor, F98, and EGFR positive tumor line, F98-EGFR, which was transfected with EGFR. In addition, we compare the uptake of ABY-029 with protoporphyrin IX (PpIX, administered as 5-aminolevulinic acid, ALA), a fluorophore currently under investigation for surgical guidance during glioma resection at Dartmouth College, and the standard of care for glioma patients in Germany. It was shown that in the EGFR positive tumor (F98-EGFR) ABY-029 outperforms PpIX in both the bulk and the margins of the tumors, while they performed the same in the bulk EGFR negative tumor (F98) and PpIX showed a slight advantage in the margin of the EGFR tumor (Elliott et al, 2016 submitted). These results show a clear indication that ABY-029 provides a surgical advantage in EGFR positive tumors.

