Biodistribution of the 100X microdose of ABY-029 was assessed in normal rats and analysis was performed at 1 hour after injection. One hour post-intravenous administration of ABY-029 the rats were sacrificed by cervical dislocation, and the organs of interest were removed and then imaged on the Pearl Imaging System (LI-COR Biosciences). We found a high accumulation of ABY-029 in the liver, skin, lungs, and kidney, which are all organs with high endogenous EGFR expression and/or that are involved in the route of excretion. No significant difference occurred between ABY-029 accumulation in male and female non-sex organs, although males had slightly higher values, possibly due to size of organ versus body weight, as injected dose was normalized to body weight. Rats without brain tumors had comparably very low levels of ABY-029 accumulation in normal brain tissue, due to the blood brain barrier.

- Pharmacokinetic Study in normal rats**

Plasma pharmacokinetics of the dye was assessed as function of time by sampling blood from a jugular vein catheter at various time points after administration. Pharmacokinetic data was collected from normal Sprague Dawley rats at time points from 1 minute to 48 hour) after intravenous injection of 100X microdose ABY-029 (244.9 µg/kg). Blood plasma was read on a Fluoromax-3 fluorimeter (Horiba Jobin Yvon), a standard curve was created, and all fluorescent data was converted to concentration using the standard curve and the bi-exponential plasma curve. The plasma curve created in this study matched closely with the previously determined pre-clinical plasma curves, indicating that the physical and biological characteristics of ABY-029 were closely retained. The plasma half-life of ABY-029 in normal rats is approximately 15-20 minutes and less than 10% remains in the plasma at 24 hours and is undetectable at 48 hours. In pre-clinical rat and mouse studies, ABY-029 has been detectable in tissues (tumor, liver, kidney) for up to 72 hours.

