6.3 Specimen Analysis

Biopsy samples taken at the time of surgery for research purposes and processed for IHC will be scored by a pathologist according to the following criteria: 0 = no staining; 1 = low membranous staining around cells; 2 = medium membranous staining completely around cells; and 3 = high membranous staining completely around cells. Standard formalin-fixation with paraffin embedding will be used for histopathologic type and grade to confirm diagnosis of astrocytoma or glioblastoma (following WHO criteria) by the study neuropathologist. As these tumors are recurrences and patients have received radiation and chemotherapy, an assessment of reactive gliosis vs. residual/recurrent glioma will also be scored as well as tumor burden and necrosis using methods previously described. Here, histopathology will be classified as non-tumor tissue, solid tumor, infiltrating tumor, or indeterminate. Infiltrating tumor will be further graded into <33% tumor, >33% but <67% tumor, and >67% tumor). Proliferation will be assessed by quantitatively scoring Ki-67 immunopositive cells. ABY-029 binding to tumor cells in the specimen will be evaluated by performing IHC with secondary antibodies directed against the anti-EGFR Affibody following the protocol. EGFR protein expression often corresponds to gene amplification, thus, we will assess gene-protein correlations on a cell-by-cell basis by performing both IHC for EGFR protein and CISH for EGFR gene amplifications using a multi-spectral analysis microscope (Nuance) to distinguish in individual tumor cells. Frozen tissue will be solubilized and evaluated for quantitative fluorescence using fluorimetry. Western and/or ELISA will be used if the signal is not sufficiently strong.

7 Statistical Plan

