7.2 Data and Statistical Analysis

The primary study objective is to relate ABY-029 fluorescence (resulting from a specific pre-surgical dose) measured by wide-field iFI to EGFR pathology score (based on IHC staining) of coregistered tissue specimens sampled at the same time points during surgery. Similar but more sensitive fluorescence data will be available from the intraoperative optical probe. A minimum of 3 patients will be enrolled at a given dose, and up to 6 patients may be enrolled at one dose, if iFI SNR requirements are met. Assuming 10 specimens are available for analysis on average from the surgical cases at a given dose (this value is consistent with average specimen counts in related ALA-induced PpIX studies which have enrolled more than 100 subjects), 30 specimens with corresponding probe signals and IHC pathological scoring will be available for analysis, and as many as 60 specimens may exist, if iFI SNR goals are achieved. Clustered

data analyses of variance will be performed to account for multiple samples from each patient. Student's t-test evaluation will be used to determine signal detectability relative to measurements in normal brain, and relative to the noise floor of the iFI system determined from laboratory measurements in phantoms. ANOVA will also be used to assess differences in signal means when stratified by EGFR pathology score (0 = no expression, 1 = low expression, 2 = medium expression, 3 = high expression). Pearson's and Spearman's rank correlations between iFI signal strength and EGFR pathology score will be computed. These analyses will be repeated for the optical probe data as well.

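### The comparison of signal across EGFR scores takes no account of tumour content, so a positive association could partly or wholly reflect tumour content or leakage

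*Combined protocol and SAP*

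**What the plan says.** Section 7.2 words the primary aim as an association: "The primary study objective is to relate ABY-029 fluorescence (resulting from a specific pre-surgical dose) measured by wide-field iFI to EGFR pathology score". The methods are an analysis of variance ("ANOVA will also be used to assess differences in signal means when stratified by EGFR pathology score", scores 0 to 3) and correlations: "Pearson's and Spearman's rank correlations between iFI signal strength and EGFR pathology score will be computed". No restriction on specimens is stated, the only adjustment named is for several samples from one patient, and the same analyses are repeated for the optical probe. Detectability is a separate test: "Student's t-test evaluation will be used to determine signal detectability relative to measurements in normal brain".

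Tumour content will be recorded. Under section 6.3, "histopathology will be classified as non-tumor tissue, solid tumor, infiltrating tumor, or indeterminate". Infiltrating tumour is split into three burden bands, and tumour burden, necrosis and reactive gliosis are also scored. In section 7.2 such indicators appear only as alternative outcomes in the secondary analyses, not as covariates or strata in the EGFR comparison.

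The synopsis (Statistical Considerations) plans to discriminate EGFR+ glioma, EGFR- glioma and normal tissue. Section 7.2 does not carry this through: the outcome of its secondary model is tumour status.

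**The concern.** Tumour content could drive both sides of the association. Section 4.2 admits only recurrent high-grade glioma that was EGFR positive at prior surgery, so score-0 specimens may come disproportionately from non-tumour or sparsely infiltrated tissue. Section 6.1 samples from first tumour exposure to near completion, at points chosen to span non-fluorescent to strongly fluorescent, so content is likely to vary widely.

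The protocol also gives reason to expect uptake without binding where the barrier is open. In rats without tumours, section 1.3.2 reports "very low levels of ABY-029 accumulation in normal brain tissue, due to the blood brain barrier". In the mouse work of section 1.3.1 a non-specific tracer "was used to quantify blood vessel leakage versus ABY-029 binding to the tumor". The same section reports a strong correlation between in vivo receptor concentration and pathologist-scored staining, obtained with a reference agent given at the same time. The human protocol describes no such agent.

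At stake is the interpretation of the association that section 7.2 calls primary. A dye that leaked into tumour without binding EGFR could also produce a positive trend.

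**Working it through.** **The plan's own figures.** Section 7.1 gives no figure for this bias. Its 1.8 SD for two EGFR levels with 6 patients reproduces as a two-sample t-test, 6 v 6, 80% power, two-sided 0.05 (1.80 SD). That match treats the patient as the unit. The illustration in step 1 is on the specimen scale, so the two are not compared.

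**Step 1. Size of a spurious difference (all inputs assumed).** Let 60% of specimens be tumour, with EGFR ≥ 1 in 80% of tumour and 10% of non-tumour specimens. EGFR has no effect on signal, and leakage raises tumour signal by L = 2 SD, in units of the SD within tissue class.

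- P(EGFR ≥ 1) = 0.6 × 0.8 + 0.4 × 0.1 = 0.52
- Tumour share if EGFR ≥ 1: 0.48/0.52 = 0.923
- Tumour share if EGFR = 0: 0.12/0.48 = 0.25
- Spurious difference: (0.923 − 0.25) × 2 = 1.35 SD

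Mixing tissue classes also inflates the spread within each EGFR group. The pooled SD is √(1 + L²[0.52 × 0.923 × 0.077 + 0.48 × 0.25 × 0.75]) = √(1 + 4 × 0.127) = 1.23. The standardised difference is therefore 1.35/1.23 = 1.10.

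| EGFR ≥ 1 in tumour / non-tumour | L | Difference, within-class SD | Difference, pooled SD |
|---|---|---|---|
| 80% / 10% | 2 | 1.35 | 1.10 |
| 80% / 10% | 3 | 2.02 | 1.38 |
| 70% / 30% | 2 | 0.77 | 0.57 |
| 70% / 30% | 3 | 1.16 | 0.69 |

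**Step 2. False-positive rate (correlations assumed).** Simulation with 10 specimens per patient (the average in section 7.2) and 3 or 6 patients. Signal depends on tumour content but not on EGFR, content has the same correlation with EGFR and with signal, and the noise has a within-patient ICC of 0.2. The ANOVA is blocked by patient. The nominal level is 5%.

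| Correlation of content with EGFR and with signal | Planned ANOVA, 3 / 6 patients | Unadjusted Spearman, 3 to 6 patients |
|---|---|---|
| 0.3 | 6% / 8% | 7-10% |
| 0.5 | 16% / 29% | 24-41% |
| 0.7 | 58% / 91% | 74-95% |

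With a five-level content factor added, the ANOVA rejects in 4-6% in every case.

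**Step 3. Limit of the adjustment.** A second simulation uses three tissue classes (non-tumour 20%, infiltrating 40%, solid 40%) and lets leakage also rise by 0.25 SD per EGFR score step within class. The content-adjusted ANOVA then still rejects in 12% / 24% (3 / 6 patients). Without that extra leakage it rejects in about 5%.

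**The case against.** The strongest reply is that the trial is a pilot of detection. The synopsis and section 2 set the objective as SNR ≥ 10 in tissue with EGFR score ≥ 1, and leaked agent would count towards that. This stands for the SNR criterion and the normal-brain t-test: the latter is already labelled detectability, and tumour content cannot be held constant against normal brain. It does not cover the ANOVA and correlations, which section 7.2 ties to its own wording of the primary objective.

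A reader might infer that leakage would be reported as EGFR-specific uptake, or that the trial could not tell the two apart. The documents do not support either reading. No passage says that the ANOVA will be taken as proof of binding. The synopsis plans the EGFR+ v EGFR- glioma contrast, section 6.3 plans IHC for bound ABY-029, and section 7.2 lists binding among its repeated analyses. What stands is that section 7.2 does not say how these bear on the EGFR comparison.

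The preclinical evidence also points both ways. Section 1.3.1 reports that highly fluorescent regions matched EGFR-overexpressing regions within tumours. Equal performance to PpIX in EGFR-negative bulk tumour does not show a shared leakage mechanism, because section 1.1 also links PpIX to increased metabolism. The make-up of score-0 specimens is an inference; biopsies come from tissue intended for resection.

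Finally, adjustment has costs. Content is only a proxy for leakage (step 3), membranous staining may itself vary with tumour-cell content so that some true EGFR signal is removed, and 30 to 60 specimens from 3 to 6 patients support few terms. These objections limit the fix but do not remove the need for it.

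**Conclusion.** The concern holds in a limited form. The EGFR-score ANOVA and correlations ignore tumour content although it is measured, so a positive association could arise partly or wholly from content or leakage. The size cannot be determined from the documents. Under assumed inputs the spurious difference is 0.57 to 1.38 pooled SD, and the ANOVA's false-positive rate runs from near nominal (6%) to about 90%. Both rest on tumour shares, leakage sizes and correlations that the plan does not give. They justify saying that the association could mislead, not that it would. Detectability and the dose decisions based on SNR are outside the point. The proposed addition is a cheap improvement to interpretation; it does not correct an invalid primary criterion.

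**What to change.** In section 7.2, keep the planned all-specimen ANOVA and correlations and add:

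- **Within-tumour contrast.** Report signal by EGFR score among tumour-bearing specimens, from the clustered model with one parsimonious tissue-content term (solid, or infiltrating by burden band) and necrosis only where numbers allow. Give estimates with intervals, and state in advance how indeterminate specimens are handled.
- **Synopsis contrast.** Specify the comparison of EGFR+ glioma, EGFR- glioma and normal tissue, with its model and outcome.
- **Bound agent.** Name the IHC for bound ABY-029 as supporting evidence.

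Limit wording about EGFR-specific uptake to these results, and state that content is a proxy for leakage and that adjustment may remove some true EGFR signal. Contrast enhancement on MRI should not be added as a covariate unless it is actually extracted at the biopsy points; the documents do not say that it will be.

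The cost is SAP wording and a few model terms on data already planned. Intervals will be wider, particularly if score-0 tumour specimens are few.

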Study Product, Dose, Route, Regimen	
Criteria for successful iFI are locations of all EGFR positive samples (defined as having a pathology score ≥ 1 based on histological staining) having a measurable signal (defined as SNR ≥ 10). A single microdose of ABY-029 at 30 nanomoles (237μg) will be injected into the first 3 patients. If samples from these subjects meet successful iFI criteria, 3 more patients will be enrolled at the same dose, concluding the study with a total of 6 subjects. Otherwise, the ABY-029 dose in the next 3 patients will be increased to 3X (90 nanomoles, 711 μg). If samples from these subjects meet successful iFI criteria, 3 more patients will be enrolled at the 3X dose, concluding the study with a total of 9 subjects. If iFI criteria are not met, the next 3 patients will be enrolled at 6X dose (180 nanomoles, 1.42 mg). If iFI criteria are met, 3 more patients will be enrolled the 6X dose, concluding the study with a total of 12 subjects. If iFI criteria are not met in the first 3 patients at the 6X dose, enrollment will be stopped with a total of 9 subjects.
 
Because of the microdosing levels used, the results of the Dartmouth Toxicity Study (at 10X, 100X, 1000X doses), and the safety profile of similar compounds (e.g. ABY-025), we do not anticipate any serious adverse events (SAEs) related to ABY-029.

Duration of administration	ABY-029 will be administered by IV injection on day of surgery, approximately 1-3 hours prior to the procedure.
Reference methods	Post-operative histopathology will serve as the gold standard.
Statistical Considerations	Repeated measures analyses of variance will be performed to account for multiple samples from each patient. Student's t-test will be used to evaluate ABY-029 fluorescence signal detection in tumor relative to normal brain with iFI and intraoperative probe. Empirical ROC curves and logistic regression analysis for clustered binary data will be used to evaluate the accuracy of ABY-029-specific fluorescence in discriminating between EGFR+ glioma tumor, EGFR- glioma tissue, and normal tissue when detected by iFI and/or intraoperative probe.

1 Introduction

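### Section 7.2 plans no analysis of iFI signal against EGFR score that both uses the 0-3 order and accounts for several specimens per patient; a clustered trend test beside the ANOVA would fill the gap

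*Combined protocol and SAP*

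**What the plan says.** Section 6.3 defines an ordered staining scale that runs up to 3 for high staining: "0 = no staining; 1 = low membranous staining around cells; 2 = medium membranous staining completely around cells". Section 7.2 opens with: "The primary study objective is to relate ABY-029 fluorescence (resulting from a specific pre-surgical dose) measured by wide-field iFI to EGFR pathology score".

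For that relation 7.2 gives two kinds of analysis.

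- **Analysis of variance.** Clustered "data analyses of variance will be performed to account for multiple samples from each patient", and "ANOVA will also be used to assess differences in signal means when stratified by EGFR pathology score". No trend contrast is named, and no model has score as an ordered or linear term. The Study Summary (Statistical Considerations) describes the method as: "Repeated measures analyses of variance will be performed to account for multiple samples from each patient".
- **Correlation.** "Pearson's and Spearman's rank correlations between iFI signal strength and EGFR pathology score will be computed". No adjustment for clustering is stated.

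The Study Summary adds a further clustered analysis: "Empirical ROC curves and logistic regression analysis for clustered binary data will be used to evaluate the accuracy of ABY-029-specific fluorescence in discriminating" EGFR-positive glioma, EGFR-negative glioma and normal tissue. It reduces the score to positive or negative. For the secondary objectives, 7.2 already specifies a generalized linear mixed model with a subject random effect and fluorescence entered as linear terms.

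**The concern.** The natural question is whether signal rises with EGFR score. An omnibus comparison of four means answers a different question, namely whether the means differ in any pattern. It yields no slope or direction, and for a steady rise it spends two extra degrees of freedom. The correlations do address the rise. But if their tests pool all specimens as independent, they can be anticonservative when both signal and score vary between patients.

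So the clustered analysis across the score levels ignores the order, and the ordered analysis is not stated to be clustered. With 3 to 6 patients per dose, at stake are a real trend being missed by the omnibus test, or a chance association being declared from pooled correlations.

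**Working it through.** **Figures in 7.1 first** (two-sided alpha 0.05, 80% power, patient as unit). A paired t-test gives 3.26 SD for 3 patients (stated 3.3) and 1.43 SD for 6 (stated 1.4). A two-sample t-test with 6 per level gives 1.80 SD (stated 1.8). With 3 per level it gives 3.07 SD, not the stated 2.7, at which power is 70%. That mismatch does not affect this point. Section 7.1 gives no power for the four-level ANOVA or for a trend.

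**Inputs.** From 7.1 and 7.2: alpha 0.05, 10 specimens per patient, N = 30 (m = 3 patients) or N = 60 (m = 6), and equal numbers at each score level. Assumed: means linear in score, one slope common to patients, patient as block, and an effect at which the trend test has 80% power.

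**Formula.** Equally used scores 0-3 have variance 1.25, so the noncentrality is lambda = N x 1.25 x slope², with slope in residual SDs per level. The slope test has (1, N - m - 1) df and the omnibus test (3, N - m - 3).

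| | 3 patients, N = 30 | 6 patients, N = 60 |
|---|---|---|
| df, slope / omnibus | (1, 26) / (3, 24) | (1, 53) / (3, 51) |
| lambda for 80% on 1 df | 8.47 (slope 0.475) | 8.14 (slope 0.33) |
| Omnibus power at that lambda | 60.3% | 62.6% |
| Loss | 19.7 points | 17.4 points |
| lambda for 80% on 3 df | 12.84 (ratio 1.52) | 11.77 (ratio 1.45) |

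Simulation with patient blocks (slopes 0.47 and 0.33) gave 74% v 55% and 75% v 57%, with both tests near 5% under the null.

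**How far the loss depends on the assumptions.**

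- *Three levels only* (2-df omnibus test): 68.8% and 69.9%, a loss of 11.2 and 10.1 points.
- *Differences in 7.1 placed between scores 0 and 3, as specimen-level SDs.* Slope 2.7/3 = 0.9 gives lambda = 30 x 1.25 x 0.81 = 30.4, and power is 99.4% v 99.96%. Slope 1.8/3 = 0.6 gives lambda = 60 x 1.25 x 0.36 = 27.0, and power is 99.3% v 99.9%. The loss is under 1 point.
- *The same differences as patient-level SDs* (one mean per patient per level; squared score deviations sum to 5). For 3 patients, lambda = 3 x 5 x 0.81 = 12.15, and power is 55% v 83-86%. For 6 patients, lambda = 6 x 5 x 0.36 = 10.8, and power is 67% v 87%. The loss is about 20-31 points.
- *Step from 0 to 1-3.* Centred means (-0.75, 0.25, 0.25, 0.25) against centred scores (-1.5, -0.5, 0.5, 1.5) give a linear share of 1.5²/(0.75 x 5) = 0.6. Where the omnibus test has 62%, the slope test has 60% (N = 30) or 58% (N = 60), so it gains nothing.
- *Non-monotone means (0, 1, 2, 1).* The linear share is 0.4, and the slope test has 44% or 42% against 62%.
- *A separate slope for each patient, 3 patients, tested on 2 df.* Where that test has 80%, the omnibus test on patient-by-level error (6 df) has 93%. The advantage therefore rests on the common-slope assumption.

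**Pooled correlations.** The documents give no intraclass correlations. Assuming 0.3-0.5 for signal and 0.3 for score, simulated type I error of pooled Pearson and Spearman tests is about 11-18% at a nominal 5%. If score does not cluster by patient, it is about 5%.

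**The case against.** A reader might infer that the plan ignores the order of the scores. It does not: pooled Pearson is itself a 1-df linear association, and Spearman is its rank counterpart. What they lack is a stated allowance for clustering, which is a type I error matter and arises only if score as well as signal clusters.

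A reader might also take 17-20 points as the plan's power loss without conditions. The documents support only the equal-allocation condition. Fewer levels are plausible, since eligibility requires EGFR-positive tissue from prior surgery. The step at score 1 or above is the protocol's own cut for EGFR positivity, and there the slope gains nothing. The under-1-point figure is less decisive, because three of the four figures in 7.1 reproduce only with the patient as unit. On that scale the loss is large.

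Nor is the ANOVA the only clustered test involving EGFR, given the logistic regression in the Study Summary. The repeated-measures label there need not mean a classical analysis requiring every score in every patient, because 7.2 speaks of clustered analyses of variance.

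Finally, Section 2 states the primary objective as SNR of at least 10 in tissue scored 1 or more, and dose and enrolment steps follow that criterion. No decision hangs on this ANOVA. That stands, and it limits the importance of the point. It does not remove it, because 7.2 still presents the signal-score relation as primary.

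**Conclusion.** The point holds in a limited form. No planned analysis of signal across the four score levels both respects their order and is stated to account for clustering. Under a linear relation, four equally filled levels, a common slope and 80% trend power, the omnibus test has about 60% (3 patients) or 63% (6 patients). The loss shrinks or disappears under other plausible conditions, so it should be quoted only with its assumptions. The inflation to about 11-18% for pooled correlation tests rests on assumed clustering of both variables. The documents do not support a claim that the ANOVA is wrong or should be dropped, or that dose selection is affected. This is an inexpensive improvement to a pilot study's analysis.

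**What to change.** In 7.2 and the Study Summary:

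- Prespecify, as the test of the signal-score relation, a linear mixed model with a patient random intercept, EGFR score as one linear term and a small-sample df correction.
- Report the slope with its confidence interval, and state the common-slope assumption.
- Keep the four-level clustered ANOVA alongside it as the check for a step or a non-monotone pattern.
- Treat pooled Pearson and Spearman coefficients as descriptive.
- Repeat for the optical probe, and use the same description of the clustered method in both places.

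The cost is wording only: no more patients, specimens or procedures, and a model type that 7.2 already uses for the secondary objectives. The downside is less power than the ANOVA if the relation is a step or not monotone (slight for the step, marked for the non-monotone pattern above), which is why the ANOVA stays. The SNR criterion and the dose decisions do not change.
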